5.1 Treatment Delay

A new course of treatment (cycle) with nanoliposomal irinotecan and temozolomide should not begin until the following criteria are met.

- Platelets $\geq 100,000 \times 10^9/L$ (100,000/mm³)
- Granulocytes (ANC) $\geq 1.5 \times 10^9/L$ (1,500/mm³)
- Recovery from other clinically significant, treatment related non-hematologic toxicities to \leq Grade 2

*please refer to section 5.2 for events that require dose reductions cycles 3-on*The treating physician may decide to hold treatment secondary to other toxicities even if deemed not related to treatment if the physician feels it is in the patient's best interest. This must be documented and submitted to BrUOG on treatment form and AE log.

If the patient does not meet these criteria at the start of a scheduled cycle, treatment should be delayed until these requirements are met.

Patients who require a treatment delay of more than 4 weeks due to toxicity will be removed from protocol treatment. Patients who require a treatment delay of more than 8 weeks not due to toxicity will be removed from protocol treatment.

If a patient is unable to receive 4 weeks of treatment (2 cycles) for reasons other than a dose limiting toxicity, they will be replaced in a cohort.

5.2 Definition of Dose Limiting Toxicities:

Dose limiting toxicities will be defined as the following toxicities occurring during the first 2 cycles (28 days) of therapies. If however a patient experiences one of the below toxicities after cycle 2 they will be dose reduced (both drugs), even though it will no longer be defined as a DLT.

- Grade 4 neutropenia (ANC < 500/mm³) for > 7 days
- ANC < 1000/mm³ with fever or infection
- Platelets < 25,000/mm³
- Platelets < 50,000/mm³ requiring transfusion
- Grade 3 or 4 treatment related non-hematologic toxicities excluding alopecia.
 - Grade 3 nausea, vomiting or diarrhea will only be considered a dose limiting toxicity if it occurs for greater than 72 hours despite maximal medical support.
 - Grade 3 electrolyte abnormalities will not be considered dose limiting toxicities if the electrolyte disorder can be corrected to grade 2 or less within 72 hours.
 - A grade 4 electrolyte abnormality will be considered a DLT.
- Delay of treatment for > 2 weeks due to toxicity (do not score a second DLT for a treatment delay caused by the same event)

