For patients who experience a second grade 1 or 2 infusion reaction, it is suggested but not required that you administer dexamethasone 10 mg IV. It is suggested that subsequent infusions should be premedicated with diphenhydramine hydrochloride 50 mg IV, dexamethasone 10 mg IV, and acetaminophen 650 mg orally.

Grade 3

- Stop infusion and disconnect infusion tubing from patient
- Administer diphenhydramine hydrochloride 50 mg IV, dexamethasone 10 mg IV, bronchodilators for bronchospasm, and other medications or oxygen as medically necessary
- No further treatment with nanoliposomal irinotecan will be permitted

Grade 4

- Stop the infusion and disconnect infusion tubing from patient
- Administer epinephrine, bronchodilators or oxygen as indicated for bronchospasm
- Administer diphenhydramine hydrochloride 50 mg IV, dexamethasone 10 mg IV
- Consider hospital admission for observation

- No further treatment with nanoliposomal irinotecan will be permitted

See section 9.1.5 for Toxicity Considerations with nanoliposomal irinotecan

6.0 SCHEDULE OF EVALUATIONS / STUDY CALENDAR* The day an assessment (PE, labs, scan etc) is completed is day 0 for counting for example labs drawn on Friday can be used for Monday dosing as this is within 3 days*

Parameter	Pre-study (to be sent to BrUOG prior to registration)	Within 3days prior to Day 1 of Each Cycle (Every 2 weeks) ^C	Every 2 months during treatment	Off study (post completion of final cycle)+ 1 week	30 days post last dose of drug (+1 week)	FU ^D
Informed Consent (within 30 days of day 1) *pts are to be re-consented if ICF will be outside 30 day window	X					
History , Demographics (baseline only)	X					
Concomitant medication log	X	X		X		
Physical examination	X	X	X	X	X ^G	X
Weight	X	X	X	X		
Vital signs	X	X	X	X		
Toxicity Assessment	X	X	X	X	XF	
Performance Status	X	X	X	X	X ^G	
CBC, diff, platelet count	X (within 14 days)	X		X		
Na, K, BUN, Cr	X (within 14 days)	X				
AST, ALT, Bili, Albumin	X (within 14 days)	X				
Serum Pregnancy ^E	X (within 7 days of drug)					
MRI brain with contrast	X ^A (within 28 days)		XH	X (not required for patients who had an MRI completed in prior 2 months)		X
EKG ^B	X					

Survival and Disease status			X		X	X
-----------------------------	--	--	---	--	---	---

^A- Brain MRI with contrast for disease assessment should be performed within 28 days of study entry. Each time: Report required to be sent to BrUOG.

^B- EKG within 8 weeks of study entry. Report required.

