^C It is appropriate to use labs from screening for cycle 1 day 1, if labs are within 14 days (pregnancy must be within 7 days of drug day 1 as noted above for applicable patients). A physical exam within 7 days prior to cycle 1 day 1 may be utilized. Weight, vitals, PS, AE and conmed assessment can be used from screening for cycle 1 day 1 if within 14 days. Labs and physical exam (with weight, vitals, PS and AEs) for all subsequent cycles can be within 3 days prior to day 1 of treatment cycle (another 1 day is given for holiday).

^D- For patients removed from protocol treatment due to toxicity(or other reason), without progression, follow-up until disease progression will include brain MRI, disease free and overall survival and physical approximately every 3 months (+/- 1 month). For patients who come off study for progression, overall survival is to be reported approximately every 3months (+/- 1 month). Follow-up will be for 2 years.

^E post-menopausal women (surgical menopause or lack of menses \geq 12 months) do not need to have a pregnancy test, document status

^F Adverse event evaluation, inclusive of SAE evaluation, and Performance status assessment will be done 30 days (+1 week) post last dose of drug . SAEs occurring outside this 30 day window must be reported if the event is considered to be possibly related to the study drug. If a patient begins a new treatment, AE evaluation will be stopped unless the patient experiences an event that is thought to be possibly related to the study drug. SAE evaluation will not be stopped if patient begins a new treatment.

^G Physical and performance status assessment to be done in coordination with 30 day toxicity assessment (+ 1 week allowed).

^H MRI of brain with contrast to be done every 2 months (approximately after every 4 cycles) +1 month window.. More frequent MRI imaging is allowed per treating MD but all information must be sent to BrUOG.

7.0 RESPONSE ASSESSMENT:

7.1 Response Definition:

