Late diarrhea (generally occurring more than 24 hours after administration of irinotecan) can be life threatening since it may be prolonged and may lead to dehydration, electrolyte imbalance, or sepsis. Late diarrhea should be treated promptly with loperamide, and octreotide should be considered if diarrhea persists after loperamide. Loss of fluids and electrolytes associated with persistent or severe diarrhea can result in life threatening dehydration, renal insufficiency, and electrolyte imbalances, and may contribute to cardiovascular morbidity. The risk of infectious complications is increased, which can lead to sepsis in patients with chemotherapy-induced neutropenia. Patients with diarrhea should be carefully monitored, given fluid and electrolyte replacement if they become dehydrated, and given antibiotic support if they develop ileus, fever, or severe neutropenia as per institutional standard practice

Neutropenia

Deaths due to sepsis following severe neutropenia have been reported in patients treated with irinotecan. Neutropenic complications should be managed promptly with antibiotic support. Patients, who are known to have experienced Grade 3 or 4 neutropenia while receiving prior anti-neoplastic therapy, should be monitored carefully and managed as outlined in the section on dose modifications and as per institutional standard practice.

Hypersensitivity

Hypersensitivity reactions including severe anaphylactic or anaphylactoid reactions have been observed. Suspected drugs should be withheld immediately and aggressive therapy should be given if hypersensitivity reactions or infusion reactions occur as outlined in section 5.4 .

Colitis/Ileus

Cases of colitis complicated by ulceration, bleeding, ileus, and infection have been observed. Patients experiencing ileus should receive prompt antibiotic support as per institutional standard practice.

Thromboembolism

Thromboembolic events have been observed in patients receiving irinotecan- containing regimens; the specific cause of these events has not been determined.

Pregnancy

The pregnancy category of irinotecan is D. Women of childbearing potential should be advised to avoid becoming pregnant while receiving treatment with irinotecan. If a pregnancy is reported, treatment should be discontinued. The patient should be withdrawn from the study, and the pregnancy should be followed until the outcome becomes known as per SAE section.

Care of Intravenous Site

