11.0 ADVERSE DRUG REACTION (ADR) REPORTING

BrUOG considers the SAE reporting period to begin when the subject signs the study specific informed consent.

This study will utilize the descriptions and grading scales found in the NCI Common Terminology Criteria for Adverse Events (CTCAE) version 4.03 for grading all adverse events. All appropriate treatment areas should have access to a copy of the CTCAE version 4.03. A copy of the CTCAE version 4.03 can be downloaded from the CTEP web site (<http://ctep.cancer.gov>).

7/21/16, 7/26/16, 8/1/16, 8/2/16, 8/3/16, 8/4/16, 8/9/16, 8/15/16, 8/16/16, 8/17/16 submitted Merrimack, 10/3/16 Merrimack edits, 10/7/16. 21
Re-submitted Merrimack 10/11/16, 11/15/16 from Merrimack, 11/17/16, 11/30/16 back to Merrimack, approved Merrimack 1/5/17,
1/26/17, 2/7/17 company review, 2/8/17, 2/13/17, 3/2/17 company, 3/3/17, approved company 3/23/17, RN/Pharmacy/EXEC review
3/31/17, 3/31/17 BrUOG, to company 4/6/17, Ipsen 4/18/17, BrUOG 4/20/17, Ipsen approved 5-4-17, FDA 5-5-17, FDA IND exemption
5/18/17, Protocol change 5/18/17, Protocol change 7/10/17 with IB v10, 8/17/17, Amendment # 1 4/6/18, Amendment #2 8/14/18,
Amendment # 3 12/8/18

An Adverse Event (AE) is defined as any untoward medical occurrence in a patient or clinical investigation subject administered a pharmaceutical product and that does not necessarily have to have a causal relationship with this treatment. An AE can therefore be any unfavorable and unintended sign (including an abnormal laboratory finding), symptom, or disease temporally associated with the use of nanoliposomal irinotecan or temozolomide whether or not considered related to Onivyde or temozolomide. This includes any newly occurring event or previous condition that has increased in severity or frequency since the administration of drug.

During clinical trials, adverse events can be spontaneously reported or elicited during open-ended questioning, examination, or evaluation of a subject. (In order to prevent reporting bias, subjects should not be questioned regarding the specific occurrence of one or more adverse events.)

Adverse events (AEs) will be recorded in the case report form for the duration of the trial, regardless of whether or not the event(s) are considered related to trial medication. All AEs considered related to trial medication will be followed until resolution even if this occurs post-trial.

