17.0 STATISTICS

SAMPLE SIZE AND STATISTICAL DESIGN

Three patients will be accrued to level 1. If no dose limiting toxicities are observed following completion

7/21/16, 7/26/16, 8/1/16, 8/2/16, 8/3/16, 8/4/16, 8/9/16, 8/15/16, 8/16/16, 8/17/16 submitted Merrimack, 10/3/16 Merrimack edits, 10/7/16. 32
Re-submitted Merrimack 10/11/16, 11/15/16 from Merrimack, 11/17/16, 11/30/16 back to Merrimack, approved Merrimack 1/5/17,
1/26/17, 2/7/17 company review, 2/8/17, 2/13/17, 3/2/17 company, 3/3/17, approved company 3/23/17, RN/Pharmacy/EXEC review
3/31/17, 3/31/17 BrUOG, to company 4/6/17, Ipsen 4/18/17, BrUOG 4/20/17, Ipsen approved 5-4-17, FDA 5-5-17, FDA IND exemption
5/18/17, Protocol change 5/18/17, Protocol change 7/10/17 with IB v10, 8/17/17, Amendment # 1 4/6/18, Amendment #2 8/14/18,
Amendment # 3 12/8/18

of 4 weeks of treatment (2 cycles) then accrual to dose level 2 will proceed. If a DLT is observed in one of the first 3 patients in a dose level, then accrual for that level will be expanded to 6 patients. Accrual will continue in this way until the MTD is determined. Two or more instances of DLT in a cohort of 6 patients will result in the preceding dose level being defined as the MTD. After determination of the MTD, the final cohort will be expanded so that a total of 25 patients are treated on study. The final cohort will be treated at the MTD.

If a patient is unable to receive 4 weeks of treatment (2 cycles) for reasons other than a dose limiting toxicity, they will be replaced in a cohort. Patients who require a treatment delay of more than 8 weeks not due to toxicity will be removed from protocol treatment.

If two or more instances of DLT in a cohort of 6 patients occurs in dose level 1 then dose level -1 of nanoliposomal irinotecan will be investigated.

Definition of Dose Limiting Toxicities

- Grade 4 neutropenia (ANC < 500/mm³)
- ANC <1000/mm³ with fever (temp > 101) or infection
- Grade 4 thrombocytopenia: Platelets <25,000/mm³
- Platelets <50,000/mm³ requiring transfusion
- Grade 3 or 4 treatment related non-hematologic toxicities excluding alopecia.
 - Grade 3 nausea, vomiting or diarrhea will only be considered a dose limiting toxicity if it occurs for greater than 72 hours despite maximal medical support.
 - Grade 3 electrolyte abnormalities will not be considered dose limiting toxicities if the electrolyte disorder can be corrected to grade 2 or less within 72 hours.
 - A grade 4 electrolyte abnormality will be considered a DLT.

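### Section 11.0 bars asking about specific adverse events and makes no exception for DLT assessment, although one DLT is defined by named symptoms and their duration

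*Combined protocol and SAP*

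**What the plan says.** Section 11.0 gives two adjoining instructions on finding adverse events. The first is permissive: "adverse events can be spontaneously reported or elicited during open-ended questioning, examination, or evaluation of a subject". The second restricts it, with the stated aim of preventing reporting bias: "subjects should not be questioned regarding the specific occurrence of one or more adverse events". Neither mentions DLTs.

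The DLT definition names symptoms. Section 5.2 states: "Grade 3 nausea, vomiting or diarrhea will only be considered a dose limiting toxicity if it occurs for greater than 72 hours". Section 17.0 repeats the item, and both add the condition that the symptom persists despite maximal medical support. The other item with a 72-hour limit is Grade 3 electrolyte abnormality, which is not a DLT "if the electrolyte disorder can be corrected to grade 2 or less within 72 hours"; that is a laboratory finding.

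The DLT window is the first two cycles (28 days). For every cycle after the first, the calendar footnote in Section 6.0 says: "Labs and physical exam (with weight, vitals, PS and AEs) for all subsequent cycles can be within 3 days prior to day 1". Section 4.0 requires each patient to be evaluated before cycle 3 and uses that evaluation to confirm DLTs. Section 11.3 requires the duration and intensity of each episode to be recorded for every adverse event, whether observed or reported.

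**The concern.** The DLT count in cohorts of 3 to 6 decides the maximum tolerated dose (MTD), which is a primary objective. The MTD is also the dose for the expansion to 25 patients. Scoring the gastrointestinal DLT needs a named symptom, its worst grade, its duration and the support given. Read literally, Section 11.0 stops staff from asking whether the patient had diarrhea, even at the visit whose purpose is to confirm DLTs.

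The restriction pushes in one direction. Following it can only leave DLT capture unchanged or lower it, and a DLT that goes uncounted makes escalation more likely. The reason given for the rule is weaker here than in a comparative trial, because there is no control arm in which reporting could differ. A missed event also matters after cycle 2, because Sections 5.2 and 5.3 tie a reduction of both drugs to the same list of events.

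**Working it through.** **Step 1: the sections side by side.**

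- *What must be known.* Sections 5.2 and 17.0: symptom, Grade 3, more than 72 hours, maximal support given.
- *When it is looked for.* Section 6.0: before each 14-day cycle. Section 4.0: again before cycle 3. An episode of just over 72 hours takes up about 3 of the 14 days, so it can start and resolve between two assessments.
- *What a visit can show after the event.* Examination, weight, vital signs, blood tests and the concomitant medication log give indirect signs. The restart rule in Section 5.1 requires recovery to Grade 2 or less, so it tests current status and not what happened earlier in the cycle.
- *What may be asked.* Section 11.0: open-ended questions, but nothing about the occurrence of a specific event.
- *What follows once an event is raised.* Section 11.3: duration and intensity. The gap is therefore in first detection, not in grading.
- *Other capture.* The only diary described is the temozolomide drug diary in Section 4.0, which serves compliance. No symptom diary, DLT checklist or scheduled contact between visits is described.

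**Step 2: direction and possible size.** The plan states no DLT rate, target DLT rate or detection rate, so there is no figure to reproduce. The formula uses the escalation rule of Sections 4.0 and 17.0 (no DLT in 3, or 1 in 3 followed by none in the next 3). It assumes that two or more DLTs in the first 3 patients also stop escalation. With q the probability that a patient has a DLT that is counted:

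P(clear) = (1 − q)³ + 3q(1 − q)² × (1 − q)³

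q = true rate × (1 − symptomatic share × share of symptomatic DLTs missed)

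All rates and shares below are assumptions.

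| True rate | Symptomatic share | Missed | q | P(clear) |
|---|---|---|---|---|
| 35% | 60% | 0 | 0.350 | 0.396 |
| 35% | 60% | 10% | 0.35 × 0.94 = 0.329 | 0.436 |
| 35% | 60% | 30% | 0.35 × 0.82 = 0.287 | 0.521 |
| 40% | 60% | 0 | 0.400 | 0.309 |
| 40% | 60% | 10% | 0.40 × 0.94 = 0.376 | 0.350 |
| 40% | 60% | 30% | 0.40 × 0.82 = 0.328 | 0.438 |
| 33% | 25% | 0 | 0.330 | 0.434 |
| 33% | 25% | 20% | 0.33 × 0.95 = 0.314 | 0.467 |
| 33% | 50% | 20% | 0.33 × 0.90 = 0.297 | 0.500 |

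First row worked: 0.65³ = 0.2746; 3 × 0.35 × 0.65⁵ = 1.05 × 0.1160 = 0.1218; sum 0.396.

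If nothing is missed, the effect is zero. For any share missed, P(clear) rises.

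**The case against.** The strongest reply is that the rule limits prompting and does not stop inquiry. Staff may ask open-ended questions, examine and evaluate; toxicity is assessed every cycle; and DLTs are confirmed before cycle 3. The symptom DLT is also hard to miss, because it counts only "if it occurs for greater than 72 hours despite maximal medical support", and a patient receiving maximal support is already in contact with clinicians. The medication log, weight, electrolytes, and reports of hospital admissions and emergency visits give further routes. Prompting has its own bias, since it can inflate counts against a fixed stopping rule even without a control arm. The case report forms are attached separately and were not available, so they may already contain prompts.

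Much of this stands, and it limits the point. It does not remove the conflict: nothing in the documents tells staff that the DLT evaluation is outside the restriction. Over-counting from prompts is also limited for this item, because a prompted symptom must still meet the grade, the duration and the support condition.

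A reader might infer more than the documents support:

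- *That DLT detection rests only on what patients volunteer.* Section 11.0 expressly allows open-ended questioning, examination and evaluation.
- *That the gastrointestinal DLT could not be scored at all.* Section 11.3 requires duration and intensity once the event is known.
- *That many DLTs are affected by the 72-hour limit.* One item names three symptoms, the electrolyte item is a laboratory result, and the hematologic items rest mainly on blood counts.
- *That the disease impairs recall.* This may be plausible, but the documents do not say so.
- *That the rule delays recognition of late diarrhea.* Section 9.1.5 warns that "Late diarrhea (generally occurring more than 24 hours after administration of irinotecan) can be life threatening", but it also calls for prompt treatment and careful monitoring. Questions at existing visits would not speed recognition between them.

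**Conclusion.** The point holds as an inconsistency with a cheap remedy. Section 11.0 restricts questions about specific events without exempting DLT assessment, whereas Sections 5.2, 17.0 and 4.0 require a DLT defined by named symptoms to be confirmed. The weakness concerns first detection of symptomatic episodes that resolve between visits.

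The direction is clear: any missed DLT favors escalation. The size is unknown. The range of 0.40 to 0.44–0.52 depends wholly on an assumed 35% true rate, an assumed 60% symptomatic share and an assumed 10% to 30% missed, and the condition of maximal support may well make the real loss smaller. These figures show how sensitive cohorts of 3 to 6 are to a few missed events. They are not an estimate for this trial.

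**What to change.** Reconcile the sections without altering any dose, DLT criterion or treatment rule.

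1. Add one sentence to Section 11.0 stating that the restriction on asking about specific events does not apply to DLT assessment.
2. At the cycle 2 visit and the pre-cycle 3 evaluation, ask directly about the symptomatic DLT items in Section 5.2: nausea, vomiting, diarrhea, fever, infection, and any other Grade 3–4 non-hematologic symptom. Record worst grade, start and stop dates, and medicines used.
3. Keep open-ended questioning for all other events.

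The cost is one sentence and a one-page form at two visits that already take place. If the separately attached case report forms already prompt for these items, only the sentence is needed. The downside is that recorded rates of these symptoms may be slightly higher than in trials that rely on unprompted reporting, which the trial report should mention.

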11.1 Definitions

An adverse event is any new, undesirable medical experience or change of an existing condition that occurs during or after treatment, whether or not considered product-related.

Serious adverse event (SAE)

Serious adverse event (SAE) is defined as one of the following:

- Is fatal or life-threatening
- Results in persistent or significant disability/incapacity
- Constitutes a congenital anomaly/birth defect
- Is medically significant, i.e., defined as an event that jeopardizes the patient or may require medical or surgical intervention to prevent one of the outcomes listed above
- Requires inpatient hospitalization or prolongation of existing hospitalization, unless hospitalization is for:
 - Routine treatment or monitoring of the studied indication, not associated with any deterioration in condition **such as the need for inpatient drug administration for observation or difficulties in transportation**
 - Elective or pre-planned treatment for a pre-existing condition that is unrelated to the indication under study and has not worsened since signing the informed consent **This must be documented and submitted to BrUOG**
 - Treatment on an emergency outpatient basis for an event not fulfilling any of the definitions of a SAE given above and not resulting in hospital admission
 - Social reasons and respite care in the absence of any deterioration in the patient's general condition

The definition of serious adverse event (experience) also includes *important medical event*. Medical and scientific judgment should be exercised in deciding whether expedited reporting is appropriate in other situations, such as important medical events that may not be immediately life-threatening or result in death or hospitalization but may jeopardize the patient or may require intervention to prevent one of the other outcomes listed in the definition above. These should also usually be considered serious. Examples of such events are intensive treatment in an emergency room or at home for allergic bronchospasm; blood dyscrasias or convulsions that do not result in hospitalization; or development of drug dependency or drug

abuse. A new diagnosis of cancer during the course of treatment should be considered an important medical event.

The definition of “related” being that there is a reasonable possibility that the drug caused the adverse experience.

Note that treatment on an emergency outpatient basis that does not result in hospital admission and involves an event not fulfilling any of the definitions of a SAE given above is not a serious adverse event. **Sites to inform BrUOG of a visit with confirmation that treating MD or PI has confirmed that ER visit does not meet above criteria, including an important medical event.**

Unexpected adverse event

An adverse event that is not mentioned in the Investigator's Brochure or package insert or the specificity or severity of which is not consistent with the investigator's brochure or package insert.

Life-threatening

Any adverse drug experience that places the patient or subject, in the view of the investigator, at immediate risk of death from the reaction as it occurred. It does not include a reaction that, had it occurred in a more severe form, might have caused death.

